## 8. ADHERENCE TO LOSARTAN

### 8.1. Methods for Monitoring Adherence:

Participants will complete a modified Morisky Scale of Adherence and ask open ended questions about adherence (qualitative measure of adherence). Participants will be given a pill bottle of losartan dispensed by a study pharmacist with the number of dispensed pills recorded (1-5 extra pills dispensed each month) by the study monitor (quantitative measure of adherence). Participants will return the pill bottles at each visit and the remaining pills will be counted to determine quantitative adherence to losartan. The study coordinator will place a reminder phone call to participants prior to their clinic appointment. Adherence will be defined as taking at least 80% of losartan doses (23 doses/4 weeks).

### 8.2 Strategies to Promote Adherence:

To evaluate the success of common strategies that promote adherence to losartan during the feasibility trial, all participants will be provided with a monthly study calendar that includes: dose/tablet number taken or missed dose, and side effects experienced that day. Participants will be asked to complete and return the calendar. Participants who do not return the calendar will be provided a stamped envelope to mail the calendar back to the study coordinator. For patients that miss >20% doses (6 missed doses/4 wks), structured qualitative interviews will be conducted to identify individual barriers to adherence.

### 8.3. Procedures for Missed appointments

If a participant misses an appointment, the study team will immediately contact the participant using the most recently provided telephone number. The study team will identify and record the cause for the missed appointment. The study team will attempt to reschedule the appointment

as soon as possible. All attempts to contact the participant and discussions with participant will be recorded in the patient record.

## 9. SAMPLE SIZE AND STATISTICAL ANALYSIS

### 9.1 Sample Size

An endpoint for this feasibility trial is to determine the effect size needed to appropriately power a definitive trial of losartan to correct nocturnal dipping, rather than efficacy of losartan. Data will be collected to understand the acceptance rate, rate of recruitment, and the drop-out rate. In preliminary fashion this feasibility trial will identify the difference in nocturnal BP improvement between the two treatment arms, and within group standard deviation of BP. The feasibility trial will evaluate the change in nocturnal dipping % from baseline in all participants and among participants receiving two different dosing strategies (intensive losartan therapy (BP <75th percentile) as compared to standard dosing (BP <95th percentile)). Sample size analysis for repeated measures and adjustments to sample size to compensate for non-adherence will occur.

The feasibility trial will enroll 40 participants with hypertension (clinic and ABPM). It is expected that 30% of the 200 cohort participants will meet eligibility criteria. Of these 60 cohort participants, we expect that 40 participants will enroll in the feasibility trial. We expect a dropout rate of <10% to ensure that the feasibility trial has > 30 participants, an accepted participant size for feasibility trials.

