### 9.2. Analysis:

Objective 1: To demonstrate in a feasibility trial the optimal dose of losartan and effect size necessary to conduct a trial of losartan in participants with abnormal nocturnal dipping.

Objective 2: Demonstrate the Acceptability of and Barriers to Enrollment into a Feasibility Trial of Losartan.

Objective 3: Demonstrate and Promote Adherence to Study Medication during Feasibility Trial

Objective 4: Demonstrate Adherence to Study Procedures and Retention in the Clinical Trial.

Analysis for Objective 1: The feasibility trial will evaluate two dosing strategies of losartan. The DSMB will be instrumental in evaluating safety of losartan during the course of the trial. At the end of the trial, the two dosing strategies for losartan will be directly compared using student's t-test. The effect size necessary to conduct a definitive trial will be obtained through identifying the acceptance rate (objective 2), adherence/dropout rate (objective 3 and 4). The correction of abnormal nocturnal dipping will be evaluated using

continuous data. To properly power a definitive trial, this feasibility trial will document the standard deviation/variability in BP among participants, the estimated difference in nocturnal blood pressure at baseline and exit.

Analysis for Objective 2: The acceptance rate will be defined by the percent of participants enrolled divided by the number of patients approached for enrollment. The acceptability of the trial will be defined by evaluating barriers or facilitators to enrolling in this feasibility trial. Dichotomous dependent variables will be created for participants that enroll or do not enroll in the study. Independent variables will reflect (ordinal) responses provided during the survey. Bivariate relationships will be tested using chi-square or Fischer's exact tests and/or logistic regression. The mentorship team will review the identified barriers and facilitators to enrollment and develop strategies to enhance enrollment in future BP trials. For example, if mistrust is a barrier, a future strategy enrollment may include peer-delivered video testimonials.

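### Sections 9.1 and 9.2 rely on this 40-participant trial for the definitive trial's effect size, make no allowance for sampling error, and derive it partly from rates that cannot give a treatment effect

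*Combined protocol and SAP*

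**What the plan says.** Section 1.1.b (Objective 3) makes sample size calculations for a phase III trial a deliverable. Section 9.1 opens with "An endpoint for this feasibility trial is to determine the effect size needed to appropriately power a definitive trial of losartan" and disclaims any aim of showing efficacy. It calls the arm comparison preliminary, but says that "this feasibility trial will identify the difference in nocturnal BP improvement between the two treatment arms", together with the within-group SD. It also plans to look at change in dipping in all participants combined. The only adjustments it names for the later sample size are for repeated measures and non-adherence.

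Section 9.2 (Objective 1) compares the arms by Student's t-test and then states: "To properly power a definitive trial, this feasibility trial will document the standard deviation/variability in BP among participants". The same sentence adds the baseline-to-exit difference in nocturnal blood pressure. Another sentence in that paragraph says the effect size for the definitive trial will be obtained from the acceptance rate and the adherence/drop-out rates.

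The number of participants rests on accrual: "It is expected that 30% of the 200 cohort participants will meet eligibility criteria", then "Of these 60 cohort participants, we expect that 40 participants will enroll in the feasibility trial", and finally "We expect a dropout rate of <10% to ensure that the feasibility trial has > 30 participants, an accepted participant size for feasibility trials". No target difference, SD, alpha or power is given. Neither section plans a confidence interval for the arm difference or the SD, and neither names a minimum worthwhile difference.

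**The concern.** An effect size estimated from a trial of this size is mostly noise. If it becomes the target difference for the phase III trial, a chance overestimate gives a trial that is far too small, and a chance underestimate gives one that is needlessly large. An estimate at or below zero gives no usable sample size. The SD carries its own error into the same formula.

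The sentence that takes the effect size from acceptance and drop-out rates is a separate fault. Those rates show how many people to approach and how far to inflate a sample size. They say nothing about how much blood pressure dipping differs between two strategies. So the one sentence that explains how the effect size will be obtained cannot be carried out as written.

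**Working it through.** **Inputs from the documents.** Cohort 200, eligibility 30%, enrolment 40 and drop-out below 10% (9.1); two arms, blocks of 6 (6.2); t-test (9.2).

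**Assumptions.** Allocation is 1:1 (the ratio is not stated). Drop-out is taken at its 10% bound. The arm difference is the planning effect. The definitive trial uses two-sided 0.05 and 80% power. The true standardised effect d is varied, because the documents give none.

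**The plan's own figures.** 200 × 0.30 = 60 eligible; 40/60 = 67% acceptance; 40 × 0.90 = 36 completers, which exceeds 30. These reproduce. There is no power calculation to check. At 1:1, 36/2 = 18 per arm.

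**Precision of the standardised difference.** SE ≈ √(2/18) = 0.333, so the 95% margin is 1.96 × 0.333 = 0.65 (0.68 with the t quantile on 34 df). With 15 per arm it is 1.96 × √(2/15) = 0.72. An observed 0.5 SD therefore has an interval of about −0.15 to 1.15. By the normal formula n = 2(1.96 + 0.84)²/d², an effect of 0.5 needs 63 per arm and 1.15 needs 12. The lower limit corresponds to no finite trial.

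**Precision of the SD.** On 34 df the 95% limits are √(34/51.97) = 0.81 and √(34/19.81) = 1.31 times the estimate. The one-sided 80% upper limit is √(34/26.94) = 1.12, and squaring gives a factor of 1.26 on sample size.

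**Sizing the next trial on the estimate.** By simulation (1,000,000 pilots of 18 per arm): draw the estimate, size a two-arm trial on it at 80% power, then compute that trial's power at the true d.

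| True d | Estimate positive | Positive and below 80% power, all pilots | Below 80%, given positive | Below 50%, given positive | Mean power, given positive |
|---|---|---|---|---|---|
| 0.3 | 82% | 50% | 61.5% | 43% | 61% |
| 0.5 | 93% | 50% | 54% | 28% | 71% |
| 0.8 | 99% | 50% | 50% | 18% | 76% |

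**Effect of pilot size (true d = 0.5).**

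| Pilot per arm | Below 80%, given positive | Below 50%, given positive |
|---|---|---|
| 18 | 54% | 28% |
| 50 | 50% | 14% |
| 100 | 49% | 6% |
| 500 | 48% | 0% |

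The frequency of a shortfall hardly moves with pilot size. Its depth does.

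**With the target difference fixed in advance (true d = 0.5, only the SD taken from 34 df).** Using the SD as estimated, 51% of definitive trials fall below 80% power but only 0.4% fall below 50%. Using the one-sided 80% upper limit of the SD, 19% fall below 80%.

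**The case against.** A reader might infer that 18 per arm is so few that a trial sized on the result will be underpowered more often than not. The calculations do not support that as a causal statement. The estimate is close to median-unbiased, so over all pilots the chance of missing nominal power is about 50% whether the pilot has 18 or 500 per arm. It rises above 50% only after non-positive estimates are set aside, and only for small to moderate effects. That conditioning is reasonable, since no trial can be sized on a non-positive estimate. Small effects are also plausible here, because both arms receive losartan from the same starting dose under the same maximum (6.1, 6.3). Even so, the excess at 0.5 SD is slight, and there is none at 0.8 SD.

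A reader might also infer that the plan commits to inserting the observed arm difference and SD as point estimates. It does not. Section 9.1 calls the comparison preliminary, and no formula is given. Section 9.2's sentence on powering names the baseline-to-exit change, and the definitive trial's comparator is never stated. If change pooled over 36 completers were the planning quantity, its margin would be 1.96/√36 = 0.33 SD of change, half the figure above. This objection stands, so the between-arm reading has to be labelled as an assumption. It does not remove the problem: on either reading the stated purpose is to power the next trial, and no allowance for sampling error is described.

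Nor do the documents support a fear that a low estimate would wrongly end the programme. They tie no progression or stopping rule to the arm difference.

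Finally, the target difference could be fixed in the definitive trial's own protocol, and the one-sided 80% limit for the SD is one convention among several. Both are fair points. They bear on how the remedy is written, not on whether the present wording is adequate.

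**Conclusion.** The point holds in limited form. Sections 9.1 and 9.2 make the planning effect for a definitive trial an output of this study, without allowance for its error. One sentence derives that effect from quantities that cannot supply it.

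On the between-arm reading, the chance of missing nominal power is about even at 0.5 SD and about 61.5% at 0.3 SD, given a positive estimate. The more serious consequence is depth: 28% and 43% of such trials respectively would have less than 50% power. These figures rest on 1:1 allocation, 36 completers, two-sided 0.05, 80% nominal power and assumed true effects. Fewer completers would make them worse. The point concerns the use made of the results; it does not question the enrolment target as a feasibility count. It should be corrected, but it does not affect the conduct of this trial.

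**What to change.** Reword 9.1 and 9.2 as follows.

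- State that the definitive trial's target difference in nocturnal dipping will be a minimum worthwhile difference, agreed with the clinical team and recorded before any outcome data from this trial are seen. Name the comparison it refers to.
- Report the arm difference and the baseline-to-exit change with 95% confidence intervals, and state that neither will serve as the planning effect.
- Take from this trial the SD with its confidence interval, the baseline-to-follow-up correlation, and acceptance and drop-out rates with exact confidence intervals. Size the definitive trial on a stated conservative value of the SD, such as an upper confidence limit.
- Delete the sentence that obtains the effect size from acceptance and adherence/drop-out rates. Keep those rates for recruitment planning and for inflating the sample size.

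This costs new wording and one clinical decision, with no change to enrolment, visits or measurements. The downside is a somewhat larger definitive trial: about 26% more participants if the one-sided 80% limit of the SD is used in place of its estimate.

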## 2.2 Randomized Feasibility Trial-

A randomized feasibility trial of losartan for the correction of abnormal nocturnal blood pressure dipping in adolescent patients with HbSS or SB0 thalassemia 11-22 years of age who have documented hypertensive blood pressure in clinic will be conducted. Participants will be randomized to losartan at doses to maintain clinic BP either <95th percentile (standard dosing strategy) or <75th percentile (intensive dosing strategy). The study will be analyzed using intention to treat for outcomes which will begin immediately after randomization to losartan. Participants will be followed monthly as standard of care with additional research procedures of performing ambulatory blood pressure monitoring at baseline, 3 months, and 6 months and urine/blood biomarkers of kidney injury at baseline, 3 months and 6 months. We propose to identify 60 eligible participants of which 40 will participate in the randomized feasibility trial. The parents/legal guardians of these children will have a one hour educational session on hypertension and kidney disease in sickle cell disease. The parents/legal guardians will be offered the opportunity to discuss hypertension and kidney disease with a Pediatric Nephrologist prior to participation in the trial.

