Analysis for Objective 3. [name] will mentor [name] in the analysis of medication adherence during a clinical trial. Specifically, the adherence rates will be reviewed for each individual participant and for all participants over time to determine feasibility of losartan adherence over the six month trial. In addition, the effect of adherence interventions (calendar, phone calls) on losartan will be reviewed as well as participant reasons stated for good/poor adherence. The mentoring team will review adherence reports and work to develop an intervention plan for enhanced adherence during the planned definitive trial.

Analysis for Objective 4: To effectively design a multicenter trial, it is vital to understand the rate and barriers to trial retention and feasibility of repeated ABPM prior to conducting a SCD hypertension trial. The retention rate will be recorded and re-evaluated against the initial Likert surveys to identify variables that may suggest future drop-out. The completion of ABPM at baseline, 3 months, and 6 months will be recorded, including days to return ABPM device. [name] will mentor [name] in analyzing the barriers in a hypertension trial.

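### Section 9.1 promises a repeated-measures sample size, but the quantities listed in 9.2 Objective 1 do not determine one, and 9.2 gives the month-3 ABPM no role beyond completion

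*Combined protocol and SAP*

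**What the plan says.** **Schedule.** Section 2.2 commits to "performing ambulatory blood pressure monitoring at baseline, 3 months, and 6 months", so each participant should have one baseline and two on-treatment recordings. The same section specifies analysis by intention to treat, starting at randomization.

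**Purpose.** Section 1.1.b, Objective 3, lists sample size calculations among the preparations for a definitive trial. Section 9.1 adds: "Sample size analysis for repeated measures and adjustments to sample size to compensate for non-adherence will occur". It does not say which trial this covers. Read with the rest of 9.1 and with 1.1.b, it most plausibly means the definitive trial.

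**Planning quantities.** Section 9.1 names "the difference in nocturnal BP improvement between the two treatment arms, and within group standard deviation of BP". It also states: "The feasibility trial will evaluate the change in nocturnal dipping % from baseline in all participants", without giving a time point. Under Objective 1 of 9.2, the quantities to be documented for powering the later trial are "the standard deviation/variability in BP among participants, the estimated difference in nocturnal blood pressure at baseline and exit".

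**Arm comparison.** Section 9.2 Objective 1: "At the end of the trial, the two dosing strategies for losartan will be directly compared using student's t-test".

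**Month 3.** In 9.2 the month-3 recording appears only under Objective 4: "The completion of ABPM at baseline, 3 months, and 6 months will be recorded, including days to return ABPM device".

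Neither section names a within-participant correlation, a covariance, an SD of change or a longitudinal model.

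**The concern.** Supplying planning parameters is a stated reason for running this trial. A sample size for repeated measures depends on how strongly a participant's recordings agree with each other, and that cannot be recovered from a cross-sectional SD and a mean difference. If the listed quantities are all that is reported, whoever sizes the definitive trial must either guess the correlation or return to the raw data.

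The second issue is the arm comparison. The natural reading of 9.2 is a t-test on month-6 data. A participant with a valid month-3 recording but no valid month-6 recording would then drop out of it, which sits poorly with the intention-to-treat statement in 2.2. Such participants are foreseeable. Section 9.1 allows for dropout, 4.2 plans interviews for those who do not complete ABPM, and 4.3 sets validity rules (at least one reading per hour including sleep, and 40 in total) that some recordings may fail.

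**Working it through.** **1. The plan's own figures.** Inputs from 9.1: 200 in the cohort, 30% eligible, 40 enrolled, dropout below 10%, more than 30 remaining.
- 0.30 × 200 = 60 eligible; 40/60 = 67% acceptance.
- 40 × (1 - 0.10) = 36, which is above 30.

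These reproduce. The 40 is an expected-acceptance figure, not a power calculation: no alpha, power, effect size, SD or correlation is stated. Everything below is therefore illustrative.

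**2. What a repeated-measures N needs, and what is listed.**

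| Needed | Listed in 9.1 or 9.2? |
|---|---|
| Difference between arms | Yes (9.1) |
| SD between participants | Yes (9.1 and 9.2) |
| Correlation between visits, or SD of change | No |
| Use of month-3 values | Completion and return time only (9.2 Objective 4) |

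**3. How much the missing quantity matters.** Assume equal variance σ² at each visit and a common correlation r. The variance of the 6-month change is σ² + σ² - 2rσ² = 2(1-r)σ². For a baseline-adjusted month-6 value the factor is 1 - r². Also assume a standardised difference of 0.5, two-sided alpha 0.05 and 80% power. Then n per arm = 2 × (1.96 + 0.84)² × factor / 0.5², about 62.8 × factor, rounded up.

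| Assumed r | 2(1-r) | Total N, 6-month change | 1 - r² | Total N, baseline-adjusted month 6 |
|---|---|---|---|---|
| 0.3 | 1.4 | 2 × 88 = 176 | 0.91 | 2 × 58 = 116 |
| 0.5 | 1.0 | 2 × 63 = 126 | 0.75 | 2 × 48 = 96 |
| 0.7 | 0.6 | 2 × 38 = 76 | 0.51 | 2 × 33 = 66 |

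For the change score 1.4/0.6 = 2.3. For the baseline-adjusted value 0.91/0.51 = 1.8. In both, N falls as r rises.

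**4. How well this trial could estimate r.** Fisher z at n = 36, r = 0.5: z = 0.549, half-width 1.96/√33 = 0.341, giving a 95% CI of about 0.21 to 0.71. For r = 0.3 it is -0.03 to 0.57, and for r = 0.7 it is 0.48 to 0.84. Carrying 0.21 to 0.71 into the change-score factor gives 2(0.79) = 1.58 down to 2(0.29) = 0.58.

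**5. What a joint model recovers here.** Dropout below 10% of 40 is fewer than four participants, and only those with a valid month-3 recording are recovered. Invalid month-6 recordings would add to this, but the documents give no rate for them.

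**The case against.** The strongest reply is that this is unspecified detail, not lost information. All three recordings are scheduled, and 4.3 has the awake, sleep and dipping values recorded, so the correlations can be computed at any time. Section 9.1 promises that the calculation will be done. That stands. A reader might infer that the trial would end without the input, or that it throws the month-3 recording away; the documents do not support either.

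A reader might also infer that month-3 values are barred from every outcome analysis. Section 9.1 gives no time point for its change from baseline, so month 3 is not expressly excluded, and the end-of-trial wording could describe when the test is run. The pairing of baseline with exit in 9.2 makes a month-6 comparison the more natural reading, but the text is ambiguous.

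Two numerical inferences should also be resisted:
- Using both on-treatment recordings does not give this trial a large gain in precision. That would come from averaging months 3 and 6. Doses start at a common level and are adjusted at monthly visits (6.1, 6.3), so month 3 may fall during titration, and a month-6 contrast is the sensible main estimate.
- A higher r does not raise the required N for this outcome. It would for an unadjusted post-treatment mean, but 9.1 names change from baseline.

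Finally, a mixed model is not needed merely to report an SD of change and correlations, and r will be imprecise at this size. Both points stand. The case for the model is that it keeps participants who lack a month-6 recording, at little cost.

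**Conclusion.** The concern holds as a gap between 9.1 and 9.2. The promised repeated-measures calculation lacks a named input, and 9.2 does not say how month-3 values are used. It is worth fixing, but it is not an arithmetic error and does not threaten the trial.

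The missing input is material: about a 2.3-fold difference in definitive N for a 6-month change score between r = 0.3 and 0.7, and about 1.8-fold if the month-6 value is adjusted for baseline. These ratios rest on assumed values of r and on equal variances across visits. The absolute N values rest further on an assumed standardised difference, alpha and power. For this trial's own arm comparison the gain is small, limited to participants without a valid month-6 recording.

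**What to change.** In 9.2 Objective 1:

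1. Replace the t-test with a linear mixed model of dipping percentage at months 3 and 6. Include baseline value, arm, visit and arm-by-visit, with an unstructured within-participant covariance. State that the month-6 arm contrast is the main estimate.
2. Report the SD of change and the 0-3, 3-6 and 0-6 month correlations with 95% confidence intervals. Name them as the inputs to the repeated-measures calculation in 9.1. Because baseline is a covariate in the model, take the two baseline correlations from the recordings themselves, within arm.
3. State in 9.1 that the interval for r will be carried into a range of sample sizes, not a single figure.

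The cost is SAP wording and a slightly longer analysis. No new visit or measurement is needed. The limitation that remains is imprecision: with 36 participants and r = 0.5, the interval of about 0.21 to 0.71 still leaves a wide range for the definitive N, and the report should say so.
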